### **3. Study Design**

The study will be a pre post pilot study to investigate whether reward processing pathways are involved in the mechanism of action of cognitive remediation (CIRCuiTS). Matched control groups will be (1) people with schizophrenia receiving treatment as usual and (2) healthy controls without a Schizophrenia Spectrum Disorder.

#### **3.1 Interventions**

**CIRCuiTs (Computerised Interactive Remediation of Cognition – Training for Schizophrenia).** This is a modular computer package including tasks of a wide range of cognitive functions (particularly executive function and memory). CIRCuiTs are run for 1 hour twice a week for 12 weeks and is delivered through a computer. CIRCuiTS consist of 40 stages. Twenty sessions are considered an adequate treatment exposure and 20 minutes a “session”.

In this study 20 participants with schizophrenia (intervention group) will have one face to face meeting with the therapist to orientate to the program. These participants will then complete the program (40 sessions or 12 weeks of at least 20-minute session twice a week) either online or in-

person, and independently or in a group. The therapist will have telephone (duration <1 hour) contact once a week to support online participation. Only the intervention group will complete these sessions.

### **3.2 Study Population**

#### **3.2.1 Intervention and treatment as usual patient groups**

Participants (n=40) with a diagnosis of a schizophrenia spectrum disorder, based on current medical records will be recruited from the teams of the Metro South Addiction and Mental Health service (MSAMHS). Participants (n=20) that are not interested in completing CR will form the patient TAU control group and will complete the pre and post measures only. Thus, group intervention allocation selection will be based on individuals' preference to participate in CR. If a participant initially signs up to the intervention group but due to change in circumstances is unable to complete CR, they will be offered the opportunity to become part of the TAU group. Individuals that initially choose to complete CR therapy but then fail to complete more than 5 sessions will be re-allocated to the control (treatment as usual) group.

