Reward Learning (RL) is a term used to identify the cognitive processes responsible to adapt behaviour following positive or negative feedback. RL is a basic adaptive function of every living organism and provides the possibility to adapt and change in response to internal and environmental demands. This process has been studied extensively in neuroscience and linked to the brain dopamine system. The dopamine hypothesis of schizophrenia is the single most influential theory in our understanding of the neurochemical basis of the illness. This theory suggests that fundamental dysregulation in this system is responsible for the illness symptoms. Dysregulation in the dopamine system is also linked to RL abnormalities which in turn are thought to influence cognitive and

negative symptoms. A growing body of basic neuroscience literature has identified two complementary and interactive neural systems in the dopamine system responsible for predicting outcome and learning from feedback (Schultz, Dayan, & Montague, 1997). The first of these systems, responsible of rapid learning, is mediated by the basal ganglia. This system, referred to as the “fast system”, is believed to represent the predicted value of actions and rewards. These predictions bias actions and underlie learning based upon positive and negative feedback. The second slower system is based primarily in the prefrontal cortex, and allows more detailed, conscious and abstract representations of values and rewards. These representations of value are instrumental in allowing individuals to flexibly respond to reward value and adapt to novelty in the environment. There is consistent evidence that people with schizophrenia are impaired at making rapid behavioural adjustments in response to feedback and that these impairments are associated with negative and cognitive symptoms (Hanssen et al., 2020; Waltz & Gold, 2007; Waltz et al., 2010). Problems using this system are evident in situations requiring rapid change in responses to environmental changes when a situation previously rewarding begins to be associated with disadvantageous outcomes. In contrast, a number of studies suggested that gradual/procedural learning system seems intact in people with schizophrenia (Schmand, Kop, Kuipers, & Bosveld, 1992), (Exner, Boucsein, Degner, & Irle, 2006) but antipsychotic medication dosage, particularly those with high levels of dopamine 2 (D2) receptors blockades, may exert a negative effect on this system.

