### **9.2 Statistical Analysis**

Participants' medication dosages will be converted to olanzapine equivalents using Leucht et al. (2016) guidelines. Outcome measures will be analysed using the SPSS Version 27 software package. A series of 3 (group: intervention, patient control; healthy control) x 2 (time: baseline, post-intervention) mixed factorial ANOVAs will be conducted to evaluate the treatment group differences for each of the outcome measures. If the normality assumption is violated, non-parametric analyses will be conducted.

Standard pre-processing of the functionally weighted images is carried out using SPM12 (<http://www.fil.ion.ucl.ac.uk/spm/software/spm8>, 2013; Friston, 2003). The pre-processing steps follows: slice timing on the functional images, to correct for differences in slice acquisition times within each volume using the middle slice as reference; realignment (estimate and reslice) on the functional images, to correct for inter-scan movement within each run (defined as >3 mm translation, >2 degrees rotation); co-registration of the functional and structural images; segmentation of the structural image, with heavy regularisation (0.1) recommended for MP2-RAGE sequence; normalization of the resliced images into a standardized, stereotaxic space (according to the Montreal Neurological Institute template); and smoothing of normalized images with a 8mm full-width-at-half-maximum isotropic Gaussian kernel.

We will adopt the General Linear Model approach for event-related designs will be conducted using SPM8 (<http://www.fil.ion.ucl.ac.uk>). For the first-level analysis task-related changes in blood-

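### The TAU group is called matched but is self-selected, and the CR v TAU contrast names no participant-level covariates, so it cannot be read as the effect of CR

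*Protocol*

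**What the plan says.** Protocol section 3 (Study Design) states: "Matched control groups will be (1) people with schizophrenia receiving treatment as usual and (2) healthy controls without a Schizophrenia Spectrum Disorder".

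Section 3.2.1 describes how the patient comparison group arises: "Participants (n=20) that are not interested in completing CR will form the patient TAU control group". It adds that "group intervention allocation selection will be based on individuals' preference to participate in CR". Patients can also enter TAU later. Those who sign up for CR but can no longer complete it are offered a place there, and those who first choose CR but "then fail to complete more than 5 sessions will be re-allocated to the control (treatment as usual) group". No section gives a variable, ratio or procedure for matching TAU patients to CR patients.

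Section 9.2 fixes the analysis of the outcome measures: "A series of 3 (group: intervention, patient control; healthy control) x 2 (time: baseline, post-intervention) mixed factorial ANOVAs will be conducted". No covariate is named. The same paragraph says that "medication dosages will be converted to olanzapine equivalents", but gives the result no use. The imaging part of section 9.2 enters head motion as a first-level regressor. It then announces second-level group comparisons of learning and neural activity, again without a participant-level covariate.

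Section 4.2 collects the CAINS, which has a motivation and pleasure scale, and the BACS. Hypothesis 1B (section 2) expects better learning in those who complete CR, and section 9.2 sets out to examine how the therapy altered learning.

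**The concern.** A matched control group suggests that the two patient groups were made alike on chosen characteristics. Here they are separated by willingness to take up a 12-week training programme, and early low attendance adds to the separation. The Introduction links reward-learning difficulty to negative symptoms and motivation, so the sorting variable plausibly lies close to what the study measures.

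If willing patients would have changed differently over 12 weeks without CR, the planned contrast would attribute that difference to CR. The word matched encourages this reading, and the planned model does nothing to guard against it.

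**Working it through.** **1. The passages side by side.** Section 3 says matched. Section 3.2.1 says preference, plus re-allocation after the start. Recruitment (section 4.1.1) is by flyers to clinicians and clinics. No described step could match a TAU patient to a CR patient. For the TAU group the label contradicts the allocation rule.

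**2. What the planned test compares.** With two time points, the group-by-time term for CR v TAU is a two-sample t-test on change = post − baseline. A stable difference *a* in level cancels: (post + *a*) − (baseline + *a*) = post − baseline. Only factors related to change can bias the contrast.

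**3. Size of the bias.** The protocol states no effect size, SD, alpha or power for this comparison, so there is no figure to reproduce. Inputs:
- 20 patients per group (section 3.2.1);
- two-sided 5% level (assumed);
- motivation gap *D*, in SD, between CR and TAU (assumed 0.5 to 1.0);
- correlation *r* of motivation with change (assumed 0.2 to 0.5);
- true CR effect zero.

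With change = *r* × motivation + √(1 − *r*²) × noise, the expected group difference is *D* × *r* in SD of change. It ranges from 0.5 × 0.2 = 0.10 to 1.0 × 0.5 = 0.50. The standard error of the difference is √(2/20) = 0.316 SD.

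False-positive rates of the unadjusted test from 20,000 simulated trials per cell:

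| *D* | *r* = 0.2 | *r* = 0.3 | *r* = 0.5 |
|---|---|---|---|
| 0.5 | 5.8% | 7.3% | 12.1% |
| 0.8 | 7.7% | 11.4% | 23.6% |
| 1.0 | 9.8% | 15.6% | 33.7% |

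With *D* = 0 the rate is 5.0% to 5.2%. With motivation as a covariate it is 4.7% to 5.3% in every cell of the table. That result assumes that the measured covariate captures the whole of the selection.

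**4. Regression to the mean.** Suppose instead that the groups differ at baseline by *D* on the outcome itself and the gap shrinks in line with a pre-post correlation ρ. The bias is *D*(1 − ρ) and the SD of change is √(2(1 − ρ)), so the standardised bias is *D*√((1 − ρ)/2). For *D* = 0.5 this is 0.22 at ρ = 0.6 and 0.16 at ρ = 0.8. For *D* = 0.8 it is 0.36 and 0.25. By normal approximation the chance of a significant result in the direction of the bias is 10.5%, 7.2%, 20.4% and 12.3% respectively, against 5%/2 = 2.5% nominal in that direction. This bias works against the group that starts higher, so it may hide a CR effect as well as imitate one.

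**The case against.** The other side has several good points.

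- **Baseline is already used.** The time factor carries each outcome's own baseline, and stable differences cancel. This stands, and it limits the point to factors related to change.
- **Covariates may be left to the SAP.** The protocol does not exclude them, and the dose conversion suggests some intended use. This stands in part. A SAP could add an adjusted model, but the protocol already names its ANOVA, and a SAP cannot repair the conflict between matched and preference.
- **This is a pilot.** Section 9.1 says it is not an effectiveness study, and section 3.2.1 discloses the preference rule. That lowers the stakes. Hypothesis 1B and section 9.2 still attribute change to CR.

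A reader might also infer more than the documents support:

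- *That the groups are known to differ in motivation.* This is plausible but not reported, and the protocol does not say why patients decline CR.
- *That the protocol says dose affects the learning under study.* The Introduction says that "antipsychotic medication dosage, particularly those with high levels of dopamine 2 (D2) receptors blockades, may exert a negative effect on this system". The system meant there is gradual, procedural learning, described as apparently intact, whereas the task in section 4.2 requires tracking and switching as reward probabilities change. Dose is a possible confounder only.
- *That the cited finding on negative symptoms proves confounding.* It reports moderation of improvement after CR, which is effect modification in treated patients. It does not show that negative symptoms predict change without CR.
- *That the ANOVA is the only outcome model.* Section 9.2 also plans second-level imaging analyses.
- *That the bias is a third to over half of the 0.45 effect in the Introduction.* That effect is for global cognition. With *D* = 0.5 and *r* = 0.3 to 0.5, the bias of 0.15 to 0.25 SD of change is 33% to 56% of 0.45 only at a pre-post correlation of 0.5. At 0.7 the SD of change is √(2 × 0.3) = 0.775, giving 0.12 to 0.19 outcome SD, or 26% to 43%. All of these inputs are assumed.
- *That ANCOVA with many covariates should replace the ANOVA.* In self-selected groups, baseline-adjusted and change-score analyses answer different questions, and neither is generally less biased. Four covariates in 40 patients is also a lot.

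**Conclusion.** The contradiction is certain from the text: TAU is labelled matched and is formed by preference and re-allocation. The planned CR v TAU contrast therefore cannot be read as the effect of CR, because selection factors related to change (motivation and negative symptoms, regression to the mean, possibly dose) remain in it.

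The size is conditional. The range of about 6% to 34% false positives instead of 5% rests on assumed motivation gaps of 0.5 to 1.0 SD and correlations with change of 0.2 to 0.5. With no gap there is no inflation. The point merits a correction of wording and an additional analysis. It does not require a change of design or removal of the ANOVA.

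**What to change.** 1. In section 3, replace matched by self-selected (non-randomised) for the TAU group, and state in section 9.2 that CR-TAU differences are associations.
2. Keep the planned ANOVA. Alongside it, pre-specify a patient-only comparison of CR and TAU adjusted for the baseline outcome and one or two priority covariates: baseline CAINS motivation and pleasure first, then olanzapine-equivalent dose. Dose belongs in a patient-only model because it is not informative in healthy controls.
3. Report unadjusted and adjusted estimates together, whichever is more favourable.

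The cost is wording and one further model on data already collected. Residual degrees of freedom fall from 40 − 2 = 38 to 40 − 4 = 36 with one covariate besides the baseline outcome, or 35 with two. The adjusted and change-score results may disagree, and the report should then say so. Covariates do not remove unmeasured willingness to engage, and they do not undo the move of low attenders into TAU. Both should be stated as limitations.

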#### **3.2.2 Healthy control group**

In addition, matched healthy controls (n=20) will be recruited from the Metro South Addiction and Mental Health community services in the Princess Alexandra Hospital district as well as from the general population via word of mouth and the snowballing effect. This will provide a benchmark to compare the clinical groups and validate the fMRI task.

### **3.3 Number of participants**

Forty individuals with a diagnosis of schizophrenia spectrum disorder and 20 healthy individuals without a diagnosis of schizophrenia spectrum disorder. Total N is 60 participants.

### **3.4 Inclusion Criteria**

#### **3.4.1 Intervention and treatment as usual patient groups**

Patients of the Metro South Addiction and Mental Health Service

Primary diagnosis of schizophrenia spectrum disorder

Basic competence in written and spoken English

Capacity to consent as advised by the treating team

Aged between 18-35

No history of neurological disorders or acquired brain injury.

Estimated intelligence quotient >70

#### **3.4.2 Healthy control group**

No history of a diagnosis of schizophrenia spectrum disorder

Basic competence in written and spoken English

Capacity to consent as advised by a member of the research team

Aged between 18-35

No history of neurological disorders or acquired brain injury.

Estimated intelligence quotient >70

### **3.5 Exclusion Criteria for all participants**

Participants known or have any suspicion that they may have a metallic object in their body. This includes things such as a cardiac pacemaker, cochlear implant, metal IUD (hormonal IUD's made of plastic are fine), neuro-stimulator, aneurysm clips, non-removable body piercing, history of shrapnel or metal fragments in the eye.

Are pregnant or possibly pregnant (unprotected sex since last menstrual period).

History of claustrophobia.

Have permanent metal braces or a molar retainer.

Weigh more than 120kg

### **3.6 Participant Information and Informed Consent**

A member of the research team will conduct the consent process. As part of the consent process the potential participant will be given the Patient Information and consent sheet. The information will also be read to the person and any questions answered by the research team member. The potential participant will be allowed as much time as they require to consent. During the consenting process, all participants will be informed that they have the right to withdraw consent from the study at any time without prejudice and withdrawal from the study will not affect their current or future care.

Revocation of consent forms will be completed for those participants who choose to withdraw from the study.

#### **3.6.1 Intervention and treatment as usual patient groups**

Consent will only be obtained from patients who are deemed to have capacity to provide informed consent by their treating team. Capacity will be determined by collaboration between the treating clinician and delegated research assistant and will comply with the guidelines within the NHMRC National Statement on Ethical Conduct in Human Research 2007. Participants under 18 years of age require parent or legal guardian consent to participate. Under 4.5.8 of the National Statement, people with a mental illness, "consent should be witnessed by a person who has the capacity to understand the merits, risks and procedures of the research, is independent of the research team and, where possible, knows the participant and is familiar with his or her condition" (e.g., Treating Clinician). We will ensure that a witness also signs the consent form. In the event where the

research assistant is unable to find a witness who is familiar with the patient, an independent witness will be used for this process. The research team will encourage the witness to be a person chosen by the potential participant and is not part of the research team.

### **3.6.2 Healthy control group**

A member of the research team will also obtain consent for the healthy control group. Consent will only be obtained from participants that meet all inclusion and exclusion criteria including a TOPF score of  $>70$ . The researcher will use clinical judgement to decide if the participant has the capacity to consent.

### **3.7 Screening assessment**

Participants who meet all inclusion criteria and none of the exclusion criteria will be invited to participate in the study. Metro South Addiction and Mental Health community medical records will provide confirmation of diagnosis for clinical participants.

## **4. Procedures**

### **4.1 Recruitment**

#### **4.1.1 Intervention and treatment as usual patient groups**

[figure not shown]
Potential clinical participants will be recruited from the Metro South Addiction and Mental Health community services in the Princess Alexandra Hospital district. Flyers advising about the study will be distributed to clinicians and placed in the community clinics to make potential participants aware of the study.

#### **4.1.2 Healthy control group**

Matched healthy controls will also be recruited from the general population via word of mouth and the snowballing effect. Flyers advising about the study will also be distributed in the community clinics to make potential participants aware of the study.

### **4.2 Measures and Assessments**

Please see Fig 1. for an outline of the study assessments and procedure.

**Fig 1. Schematic of study design**

**Life Skill Profile (LSP – 16)** The Life Skills Profile - 16 (LSP - 16) was developed by an Australian clinical research group to assess a consumer's abilities with respect to basic life skills. Its focus is on the consumer's general functioning and disability rather than their clinical symptoms. There are 16 items, with a anchored four-point scale. Higher scores indicating a greater degree of disability (i.e. a score of 3 represents greater dysfunction and a score of 0 represents good functioning). A total LSP scale score is calculated by adding individual scores for the whole scale together. Therefore, for the LSP-16, the total score can range from 0 to 48. Items with missing data

are excluded from the calculation. Test of Premorbid Function (TOPFF) (Wechsler, 2009) is based on a revision of the Wechsler Test of Adult Reading (WTAR) and provides an extended intelligence quotient (IQ) range of prediction of premorbid IQ.

**Brief Assessment of Cognition in Schizophrenia (BACS)**(Atkins et al., 2016).The Brief Assessment of Cognition in Schizophrenia (BACS) was developed to assesses the aspects of cognition found to be most impaired and most strongly correlated with outcome in patients with schizophrenia. The BACS require less than 35 min to complete in patients with schizophrenia. The BACS was found to be as sensitive to cognitive impairment in patients with schizophrenia as a standard battery of tests that required over 2 h to administer.

**Schizophrenia Cognition Rating Scale (SCoRS)** is a 20-item interview-based clinical assessment that evaluates cognitive deficits and the degree to which these deficits impair patients' day-to-day functioning ref. The SCoRS assessment collects information generated from three different sources: (1) An interview with the patient, (2) an interview with an informant for the patient (ideally a person who has regular contact with the patient in everyday situations, such as a family member, friend, or social worker), and (3) a rating based on the clinical judgement of the clinician who administered the scale to the patient and informant. In addition to the 20 individual items, there is also a global rating assigned by the clinician.

**Clinical Assessment Interview for Schizophrenia (Schizophrenia (CAINS)**(Forbes et al., 2010) The Clinical Assessment Interview of Negative Symptoms (CAINS) is a measure of negative symptoms of schizophrenia comprising two scales with nine items rating the category of motivation and pleasure and four items rating the category of expression. The time frame for ratings is the past one week. The anchor points go from 0 no impairment to 4 severe impairments. The ratings are based on a semi structured interview.

**Calgary Depression Scale for Schizophrenia (CDSS)** (Addington, Addington, & Maticka-Tyndale, 1993). The CDSS was developed specifically to assess depression in people with schizophrenia. It is a nine-item semi structured clinician rated scale.

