## **9. Data and analysis**

### **9.1 Sample Size and Power**

This is a pilot study to assess possible mechanism of effect of CR and the fMRI task in examining neural pathways involved in motivation not an effectiveness study.

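### The LSP-16 total is a plain sum that leaves out missing items, so each missing item counts as 0, the best score, and incomplete forms can only look less disabled or unchanged

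*Protocol*

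**What the plan says.** The LSP-16 paragraph of Protocol section 4.2 fixes five things.

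- Items: "There are 16 items, with a anchored four-point scale".
- Direction: "a score of 3 represents greater dysfunction and a score of 0 represents good functioning".
- Total: "A total LSP scale score is calculated by adding individual scores for the whole scale together".
- Range: "Therefore, for the LSP-16, the total score can range from 0 to 48".
- Missing items: they "are excluded from the calculation". The sentence runs across a page break but is complete.

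The paragraph gives no proration, no item-mean score and no minimum number of answered items, and no other section of the protocol supplies one.

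Section 9.2 then states that 3 (group) by 2 (time) "mixed factorial ANOVAs will be conducted to evaluate the treatment group differences for each of the outcome measures". It does not name the LSP-16.

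**The concern.** Dropping an unanswered item from a mean is neutral if that item resembles the answered ones. Dropping it from a sum is not neutral, because it adds 0, and on this scale "a score of 0 represents good functioning". The error in a single total has one direction: towards less disability. Totals built from different numbers of items are then analysed as though they lay on one scale.

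What is at stake is the comparison over time and between the patient groups. Section 3.2.1 allocates patients by preference and allows re-allocation, so randomisation does not help to balance form completeness. If more items are missing after the intervention period than before it, or in one group than in the other, the difference enters the group by time contrast as apparent functional change. The opposite pattern would conceal a real gain.

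**Working it through.** **Inputs from the protocol (section 4.2):** 16 items; item score 0 to 3; total = plain sum; missing items left out.

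**Inputs assumed, because the protocol gives none:** mean item score m from 0.5 to 2; number of missing items k from 1 to 4; share of forms affected.

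**Step 1. The stated range.** 16 × 0 = 0 and 16 × 3 = 48. This reproduces the stated 0 to 48 for a complete form.

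**Step 2. What exclusion does.** With k items missing, the recorded total is the sum of the 16 − k answered items. That equals the 16-item sum with the k missing items set to 0. The shortfall is the sum of the true scores of the missing items, which lies between 0 and 3k. No assumption is needed for this step.

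**Step 3. Attainable maximum, (16 − k) × 3.**

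| Items missing (k) | Maximum total |
|---|---|
| 0 | 48 |
| 1 | 45 |
| 2 | 42 |
| 3 | 39 |
| 4 | 36 |

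**Step 4. Expected loss, if missing items resemble answered ones (assumption).** The full total is 16m and the recorded total is (16 − k)m. The loss is km, a fraction k/16 of the total: 6.25%, 12.5%, 18.75% and 25% for k = 1 to 4.

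| Item mean m | Full total | Loss, k = 1 | Loss, k = 2 | Loss, k = 4 |
|---|---|---|---|---|
| 0.5 | 8 | 0.5 | 1 | 2 |
| 1.0 | 16 | 1 | 2 | 4 |
| 1.5 | 24 | 1.5 | 3 | 6 |
| 2.0 | 32 | 2 | 4 | 8 |

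**Step 5. Effect on change, illustrated at m = 1.5 with no true change.** A complete baseline form and two items missing afterwards give 24 then 21, an apparent improvement of 3 points. Two items missing at baseline and a complete form afterwards give 21 then 24, an apparent worsening of 3 points. The artefact can run either way.

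**Step 6. Effect on a group mean.** If 25% of forms in a group lack two items at m = 1.5, the group mean is too low by 0.25 × 2 × 1.5 = 0.75 points.

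**Step 7. The repaired score.** Prorated total = 16 × (sum of answered items)/(16 − k). For k = 2 and m = 1.5 the answered sum is 14 × 1.5 = 21, and 16 × 21/14 = 24. The 0 to 48 range is restored. For k = 0 the formula returns the plain sum.

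**The case against.** The strongest reply concerns weight. Every aim and hypothesis in section 2 concerns reward learning, neural activity or working memory, and none names the LSP-16 or functioning. Section 9.1 says: "This is a pilot study to assess possible mechanism of effect of CR". The LSP-16 is not named as a primary outcome. All of this stands, and it keeps the point minor.

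Three stronger readings are tempting, and the protocol does not support them.

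- A reader might infer that the analysis will show a functional gain that is not real. Nothing in the protocol indicates how many items will be missing, or that completeness will differ by visit or group. If it does differ, the artefact may equally hide a gain.
- A reader might infer that each missing item costs exactly one sixteenth of the total. That holds only if missing items resemble answered ones. The actual loss is the item's true score, which may be nothing.
- A reader might infer that the stated range is contradicted. An incomplete form still gives a total between 0 and 48; only its attainable maximum falls.

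It can also be said that proration and completeness thresholds are details for a statistical analysis plan, which is not shown here. That would answer a complaint about silence. Here the protocol states a rule, and the rule gives a biased score. An analysis plan that prorated would depart from section 4.2, so the sentence would still need changing. Whether the instrument's own scoring guidance prorates cannot be checked from this document.

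**Conclusion.** The point holds as a minor scoring defect in a measure tied to no stated aim. It is certain that, under the rule as written, a missing item counts as 0, that totals from incomplete forms are lowered or unchanged by 0 to 3 points per missing item, and that the attainable maximum drops by 3 points per missing item.

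The practical size is not certain. It depends on how many items are missing, what their true scores would have been, and whether completeness differs by visit or group. The protocol informs none of these. Under the assumption of similar items, two missing items cost 1 to 4 points over item means of 0.5 to 2. The mechanism aims and the imaging analysis do not depend on this score.

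**What to change.** In section 4.2, replace the sentence on missing items with a rule of this form: the LSP-16 total is 16 times the mean of the answered items when at least a prespecified number of the 16 items is answered; otherwise the total is missing. A minimum of 13 of 16 is offered only as an example; it has no source in the protocol, and any sensible minimum fixed before scoring would serve.

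The cost is one sentence and one line of scoring code, and complete forms score exactly as before. There are two limits. Proration removes the bias only so far as missing items resemble answered ones. A total set to missing also has a consequence in section 9.2: the planned mixed factorial ANOVA would normally drop a participant who lacks the total at one visit. A reader might expect a mixed model to absorb that gap, but the protocol plans a mixed factorial ANOVA, not a likelihood-based mixed model. With 20 patients per group, it is worth reporting how many LSP-16 forms were incomplete and how many participants were lost for this reason.
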